9.2. Adverse Events

9.2.1. Definition and Classification of Adverse Events

AEs are defined as those AEs occurring on or worsening in severity after the first dose of any study drug (i.e., the conventional treatment-emergent AEs). Only AEs as described above are collected in the study database. All AEs are reported since the first dose of any study drug until end of safety follow-up (30 days after the last dose of study drug). SAEs thought to be related to a study specific procedure are also collected between the time the patient signs the informed consent and the first dose of any study drug.

AEs will be coded from verbatim text to PT and grouped by primary SOC according to MedDRA version 26.1 or later. The severity (toxicity grades 1-5) of AEs will be graded according to the NCI CTCAE version 5.0 by the Investigator.

Hematologic Adverse Events

AEs related to hematologic toxicity will be collapsed based on the PTs from MedDRA version 26.1 or later and will be summarized separately (see Section 9.2.3). Table 8 outlines those PTs that will be collapsed.

Term presented in the Output	Preferred Term
Neutropenia	Neutropenia
	Neutrophil count decreased
Anemia	Anemia
	Anaemia
	Red blood cell count decreased

Table 8	Hematologic Preferred Terms to be Collapsed
---------	---

Term presented in the Output	Preferred Term		
	Hemoglobin decreased		
Thrombocytopenia	Thrombocytopenia		
	Platelet count decreased		
Lymphocytopenia	Lymphocytopenia		
	Lymphopenia		
	Lymphocyte count decreased		
Leukopenia	Leukopenia		
	White blood cell count decreased		

Trilaciclib Adverse Events of Special Interest

AEs of special interest (AESI) for trilaciclib have been identified, reflecting either the findings in the AEs from the previous studies of trilaciclib or class effects for CDK 4/6 inhibitors. AESI for trilaciclib will be identified by searching MedDRA PTs based on the Customized MedDRA Queries as detailed in Appendix 2.

Specifically, trilaciclib AESI include the following 5 categories:

- Injection site reaction/Phlebitis/Thrombophlebitis
- Acute drug hypersensitivity reaction
- Hepatotoxicity
- Interstitial lung disease /Pneumonitis
- Embolic and thrombotic events, venous

9.2.2. Imputation Rules for Missing Start or Stop Date for Adverse Events

AEs with start/stop dates that are partially or completely missing that are not ongoing at the time

of data cutoff will be imputed according to the specifications below in order to classify AEs.

For completely missing or partially missing AE start date:

- If the start date has month and year but day is missing, the first dose date of any study drug will be used if the month and year is the same as the first dose date, otherwise, the first day of the month will be used.
- If the start date has year, but day and month are missing, then the first dose date of any study drug will be used if the year is the same as the first dose date, otherwise January 1st will be used.
- If the start date is completely missing, then it will be imputed as the first dose date of any study drug.

After the imputation, the imputed start date will be compared with AE stop date, if available. If the imputed start date is later than the stop date, the start date will be imputed with the stop date instead.

For completely missing or partially missing AE stop dates:

- If the stop date has month and year but day is missing, the last day of the month will be used.
- If the stop date has year, but day and month are missing, December 31st will be used.
- If the stop date is completely missing, the date of EOT visit will be used; if EOT visit does not exist, then the last dose date + 14 days will be used.

After the imputation, the imputed AE stop date will be compared against the death date for patients who died. If the date is later than the death date, the date of death will be used to impute the stop date instead.

Every attempt will be made to obtain complete information for AEs regarding severity (i.e., CTCAE Grade) and relationship to drug. However, in the rare case of missing data, the following conservative approach will be taken for summary purpose. The non-imputed raw data will be presented in AE listings.

- Missing AE grade will be classified as "Grade 3"
- Missing AE relationship will be classified as "Related"

9.2.3. Analysis for Adverse Events

AEs will be summarized by number and percentage of patients having at least one occurrence at the PT and SOC level overall. Patients with more than one occurrence of the same SOC (PT) will be counted only once within the SOC (PT) categorization. In general, the percentage of patients with an event will be calculated using the number of patients in the safety population as the denominator.

AEs will also be summarized by CTCAE grade and relationship to study drug (to any study drugs and to each individual study drug). Should a patient experience more than one occurrence of the same SOC (PT), the patient's worst occurrence (highest grade or highest related causality) will be used for the analysis and reporting.

In AE summaries, the SOC and PT within a SOC will be presented in descending order based on the incidence from all patients. If the incidence for two or more PTs is equal, these PTs will be presented in an alphabetical order.

An overall AE summary table will be generated to present general information related to AEs including the following categories: number and percentage of patients with any AE, Serious AEs, AEs with CTCAE Grade \geq 3 or 4, AEs leading to discontinuation of any study drug, AEs leading to death, AEs related to study drug (to any study drug, to trilaciclib/placebo, and to each other study drug), and AESI for trilaciclib/placebo.

In addition, the following summary tables will be generated, and they will be, in general, presented by SOC and PT unless otherwise specified.

- 1. AEs by decreasing frequency of PT
- 2. AEs by SOC, PT, and CTCAE Grade
- 3. AEs with CTCAE Grade 3 or 4 by SOC and PT
- 4. AEs leading to discontinuation of any study drug
- 5. AEs leading to death
- 6. AEs related to any and each study drug
- 7. Hematological AEs by collapsed PT and CTCAE grade
- 8. Serious AEs
- 9. Serious AEs related to any and each study drug
- 10. AESI for trilaciclib

In the above, hematological AEs will be reported as they are with the exception of item 7 (Hematological AEs by collapsed PT and CTCAE grade), for which the collapsed terms as specified in Table 8 (Section 9.2.1) will be reported.

Corresponding AE listings will be provided to clearly indicate, at the patient level, the AE and SAE occurrence, start/stop date, relative study days to onset or stop, grade and causality for each AE. AESI for trilaciclib/placebo will also be listed with a similar level of detail.

9.3. Clinical Laboratory Data

9.3.1. Laboratory Parameters

Blood and urine samples for the determination of clinical chemistry, hematology, and urinalysis laboratory variables described in Table 9 will be measured according to Schedule of Assessments in Appendix 1.

Lab Category	Lab Parameters
Chemistry	albumin, alkaline phosphatase (ALP), total bilirubin, calcium, chloride, creatinine, glucose, inorganic phosphorus, potassium, total protein, alanine aminotransferase (ALT), aspartate aminotransferase (AST), lactate dehydrogenase (LDH), sodium, blood urea nitrogen (BUN)
Hematology	hemoglobin, white blood cell (WBC), platelet counts, absolute neutrophil count (ANC), absolute lymphocyte count (ALC)
Urinalysis	semiquantitative dipstick: specific gravity, pH, evaluation of glucose, protein, bilirubin, ketones, leukocytes, and hemoglobin microscopic examination, including red blood cell (RBC), white blood cell (WBC), and casts will be performed, if necessary

 Table 9
 Laboratory Categories and Parameters

Lab = laboratory.

For hematology parameters, if absolute counts are not provided, those values will be derived from the differential counts by multiplying differential value with leukocyte value from the same sample. The normal ranges will be left missing in those cases.

Clinical chemistry and hematology assessments will be graded according to NCI CTCAE criteria, Version 5.0 or later. The determination of CTCAE grade for each measurement will be based on the collected laboratory values and will not involve clinical judgement. For laboratory parameters that CTCAE toxicity grade are not available, they will not be included in the analyses in which toxicity grades are reported. Instead, these parameter results will be classified and reported by the low/normal/high based on the laboratory normal reference ranges.

Abnormal Hepatic Laboratory Values

Abnormal hepatic laboratory values are defined in the following categories including any occurrence among all on-treatment, post-baseline assessments including scheduled and unscheduled values.

- Hy's Law:
 - Alanine aminotransferase (ALT) and/or aspartate aminotransferase (AST) > 3x the upper limit of normal (ULN), alkaline phosphatase (ALP) < 2xULN, and total bilirubin ≥ 2xULN
 - Preexisting baseline ALT, AST, OR total bilirubin values above the upper limit of normal, and the patient subsequently presents with:
 - AST or ALT ≥ 2 times the baseline values and $\geq 3 \times ULN$, or $\geq 8 \times ULN$ (whichever is smaller)
 - **concurrent** with total bilirubin ≥ 2 times the baseline value OR $\ge 3 \times ULN$ (whichever is smaller)
- AST: > 3 and $\le 5x$ ULN, > 5 and $\le 8x$ ULN, > 8 and $\le 10x$ ULN, > 10 and $\le 20x$ ULN, and > 20x ULN; AST > 5x ULN for more than 5 weeks.
- ALT: >3 and \leq 5x ULN, > 5 and \leq 8x ULN, > 8 and \leq 10x ULN, > 10 and \leq 20x ULN, and > 20x ULN; ALT > 5x ULN for more than 5 weeks.
- Total bilirubin > 1.5xULN and < 2xULN, ≥ 2 xULN

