## 7.1. Inclusion Criteria

Patient eligibility should be reviewed and documented by an appropriately qualified member of the Investigator study team before patients are included in the study. Patients must meet *all* of the following inclusion criteria to be eligible for enrollment into the study:

- 1. Age ≥18 years.
- 2. Female or male patient with measurable, unresectable locally advanced or metastatic TNBC.
- 3. Documentation of histologically or cytologically confirmed hormone (estrogen and progesterone) receptor negative tumor by immunohistochemistry (IHC) assessment (defined as <1% nuclei staining) and HER2-negative, non-overexpressing (by IHC [0 or 1+] OR in situ hybridization [ratio <2.0] OR average HER2 gene copy number of <4 signals/nucleus) per 2018 American Society of Clinical Oncology (ASCO) and the College of American Pathologists (ASCO/CAP) criteria. Patients with "estrogen receptor (ER) or progesterone receptor (PR) low positive" as per updated ASCO/CAP 2020 guidelines can be considered after approval by the Medical Monitor.
- 4. Measurable disease as defined by RECIST v1.1.
- 5. Considered to be eligible to receive sacituzumab govitecan-hziy treatment, in the Investigator's judgment.
- 6. Patients must have received 2 or more prior lines of systemic therapy, at least one of them in the metastatic setting.
- 7. Radiation therapy for metastatic disease is permitted as long as the patient has at least 1 measurable lesion that has not been irradiated. Patients should be sufficiently recovered from the effects of radiation as determined by the Investigator but must have completed radiotherapy at least 2 weeks prior to enrollment.
- 8. ECOG performance status of 0 or 1.
- 9. Adequate organ function as demonstrated by the following laboratory values:
  - a. Hemoglobin ≥9.0 g/dL in the absence of RBC transfusion or ESA administration within 7 days prior to the first dose of trilaciclib;
  - b. Absolute neutrophil count (ANC)  $\geq 1.5 \times 10^9$ /L;
  - c. Platelet count  $> 100 \times 10^9 / L$ :
  - d. Estimated glomerular filtration rate >30 mL/minute/1.73 m^2;
  - e. Total bilirubin  $\leq 1.5 \times$  upper limit of normal (ULN);
  - f. ALT and AST  $\leq$ 3 × ULN in the absence of liver metastasis or  $\leq$ 5 × ULN in the presence of liver metastasis.

G1T28-213

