## 9.3.3. Hy's Law Management

Abnormal values in AST and/or ALT concurrent with abnormal elevations in total bilirubin that meet the criteria outlined below in the absence of other causes of liver injury are considered potential cases of drug-induced liver injury (potential Hy's Law cases) and should always be considered important medical events.

The threshold of laboratory abnormalities for a potential case of drug-induced liver injury depends on the patient's individual baseline values and underlying conditions. Patients who present with the following laboratory abnormalities should be evaluated further to determine the etiology of the abnormal laboratory values:

- Baseline AST or ALT and total bilirubin values are within the normal range and
  the patient subsequently presents with AST or ALT ≥3 × ULN concurrent with a
  total bilirubin ≥2 × ULN with no evidence of hemolysis and an alkaline
  phosphatase ≤2 × ULN or not available.
- Preexisting ALT OR AST OR total bilirubin values above the upper limit of normal, and the patient subsequently presents with:
  - AST or ALT  $\geq$ 2 times the baseline values and  $\geq$ 3 × ULN, or  $\geq$ 8 × ULN (whichever is smaller)
  - Concurrent with total bilirubin increased by one time the baseline value OR >3 × ULN (whichever is smaller).

The patient should return to the investigational site and be evaluated as soon as possible, preferably within 48 hours from awareness of the abnormal results. This evaluation should include laboratory tests, detailed history, and physical assessment. In addition to repeating AST and ALT, laboratory tests should include albumin, creatine kinase, total bilirubin, direct and indirect bilirubin, gamma-glutamyl transferase, prothrombin time/International Normalized Ratio (INR), and alkaline phosphatase. A detailed history, including relevant information, such as review of ethanol, acetaminophen, recreational drug and supplement consumption, family history, occupational exposure, sexual history, travel history, history of contact with a jaundiced patient, surgery, blood transfusion, history of liver or allergic disease, and work exposure, should be collected. Further testing for acute hepatitis A, B, or C infection and liver imaging (e.g., biliary tract) may be warranted.

G1T28-213

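### The SAP's first Hy's law limb omits the protocol's normal-baseline condition, so a stable pre-existing ALT/AST elevation can be flagged as a case

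*SAP*

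**What the plan says.** Protocol 9.3.3 (Hy's Law Management) sorts patients by baseline.

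- **Limb 1** applies when "Baseline AST or ALT and total bilirubin values are within the normal range". It is met if "the patient subsequently presents with AST or ALT ≥3 × ULN concurrent with a" bilirubin of at least 2×ULN, hemolysis is not evident, and the alkaline "phosphatase ≤2 × ULN or not available".
- **Limb 2** starts from "Preexisting ALT OR AST OR total bilirubin values above the upper limit of normal, and the patient subsequently presents with" a transaminase rise judged against the patient's own baseline, together with a bilirubin rise judged the same way.

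SAP 9.3.1 (Abnormal Hepatic Laboratory Values) also has two entries under Hy's law. The first requires ALT and/or AST above 3×ULN, "alkaline phosphatase (ALP) < 2xULN, and total bilirubin" of at least 2×ULN. It states no baseline condition and no timing link. All the hepatic categories sit under a lead-in that counts any occurrence among on-treatment, post-baseline assessments. The second entry keeps the abnormal-baseline condition, the relative thresholds and the requirement that the two rises be concurrent.

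SAP 9.3.2 plans a count and percentage for each hepatic category and a separate listing of patients who met Hy's law. SAP Section 10 (Changes from the Protocol) does not mention the Hy's law definition.

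Protocol 7.1, criterion 9f, admits patients with ALT and AST up to 5 × "ULN in the presence of liver metastasis" and up to 3×ULN otherwise. Criterion 9e allows total bilirubin up to 1.5×ULN.

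**The concern.** The protocol's second limb stops a pre-existing, disease-related transaminase elevation from counting as a new liver signal. In the SAP the limbs are alternatives and the first is open to everyone. A patient with an abnormal baseline who would fail the relative test can therefore be flagged through limb 1.

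Hepatotoxicity is one of the trilaciclib AESI categories (SAP 9.2.1), and protocol 4.3.3.1 states that no Hy's law case had been reported with trilaciclib. Against that background, even one patient in this table would attract attention. The other omissions in limb 1 work in both directions: some could add cases and some could remove them.

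**Working it through.** No figure in the plan is available to reproduce, because this is a comparison of definitions.

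**Step 1. The first limbs side by side.**

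| Element | Protocol 9.3.3, limb 1 | SAP 9.3.1, limb 1 |
|---|---|---|
| Baseline | AST or ALT, and bilirubin, normal | none stated |
| ALT/AST | ≥3×ULN | >3×ULN |
| Bilirubin | ≥2×ULN | ≥2×ULN |
| Timing | concurrent | not stated |
| ALP | ≤2×ULN, or not available | <2×ULN |
| Hemolysis | none evident | not mentioned |

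The second limbs agree in substance. A bilirubin increase of one time the baseline value is the same as reaching twice baseline. The only difference is the alternative bilirubin cut-off: >3×ULN in the protocol and ≥3×ULN in the SAP.

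**Step 2. How far limb 1 bypasses limb 2.** Let b be baseline ALT in multiples of ULN. Limb 2 needs on-study ALT of at least T(b) = min(max(2b, 3), 8).

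- b = 1.5: T = 3
- b = 2: T = 4
- b = 3: T = 6
- b = 4: T = 8
- b = 5: 2b = 10, capped at T = 8

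SAP limb 1 needs only ALT above 3×ULN. For any baseline above 1.5×ULN there is a band, from just above 3×ULN up to T(b), in which limb 1 accepts what limb 2 would reject. At b = 4 or 5 the band runs up to 8×ULN.

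**Step 3. Hypothetical profiles (assumed values, multiples of ULN).** The SAP lead-in can be read two ways: components may come from different visits, or one visit must meet them all.

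| Profile | Protocol | SAP, across visits | SAP, same visit |
|---|---|---|---|
| A. Normal baseline; ALT 4, bilirubin 2.5, ALP 1 at one visit | yes | yes | yes |
| B. Baseline ALT 4, bilirubin 1.2; on study ALT 4, bilirubin 2.1, ALP 1 | no | yes | yes |
| C. Normal baseline; ALT 4 at one visit, bilirubin 2.5 at another, ALP 1 at both | no | yes | no |
| D. Normal baseline; ALT 4, bilirubin 2.5, no ALP value at all | yes | no | no |
| E. Normal baseline; ALT exactly 3, bilirubin 2.5, ALP 1 | yes | no | no |
| F. Normal baseline; ALT 4, bilirubin 2.5, ALP exactly 2 | yes | no | no |

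Profile B is the main finding: 2 × 4 = 8, and ALT of 4 falls short of 8, yet limb 1 flags the patient on either reading. The result is the same with bilirubin 2 and ALP 1.5, because the protocol's ALT test still fails. Profile C depends on the across-visits reading. In profile D, SAP 9.1 generally does not impute missing safety data, so an absent ALP cannot satisfy <2×ULN.

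**Step 4. Size.** One patient misclassified among the 30 enrolled is 1/30 = 3.3%.

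**The case against.** The case against has several parts, and much of it stands.

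- **Concurrency and missing ALP pull against each other.** Across visits, an ALP missing at one visit loses nothing if another on-treatment value is below 2×ULN. On a same-visit reading the concurrency problem disappears. Limb 2 says concurrent under the same lead-in, so the lead-in may mean only that one qualifying assessment is enough. This stands: neither omission should carry the point. The baseline omission does not depend on the reading.
- **Missing ALP should be uncommon.** It belongs to the same chemistry panel as AST, ALT and bilirubin (protocol 17.1), and the 9.3.3 work-up measures it again. The documents give no rate of missing values.
- **The SAP supersedes the protocol on analysis methods (SAP Section 1).** This settles which rule is programmed. It does not explain an unlisted difference in Section 10.
- **The effect is visible.** A Hy's law listing and full laboratory listings are planned, so an over-flagged patient could be recognised from the baseline. This lessens the harm but leaves the tabulated count unchanged.

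A reader might infer that the table will contradict the reported SAEs. The documents do not support that comparison: SAE reporting under 9.3.3 also requires confirmation on repeat testing and no other identified cause, so a laboratory table need not equal the SAE count even when the definitions agree. A reader might also infer that patients with liver metastases meet the ALT/AST part at every visit. Criterion 9f is a ceiling, and the inference holds only for a patient who stays above 3×ULN. Nor would a true case vanish from the report, since site SAE reporting does not depend on the SAP rule.

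**Conclusion.** The point holds in a limited form. SAP limb 1 lacks the protocol's normal-baseline condition, and this alone makes a patient with a stable ALT of 4×ULN and bilirubin reaching 2×ULN a case under the SAP but not under the protocol, however the visits are combined. The remaining differences (concurrency, unavailable ALP, hemolysis, two boundary signs) are secondary and can raise or lower the count.

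The conclusion is that the table and listing may not match the protocol's laboratory criteria. It is not that they will. The documents do not say how many patients entered with raised ALT/AST, and with 30 patients and no earlier Hy's law cases both counts could be zero. The 3.3% is the weight of one hypothetical patient and not an expected error. The primary PFS analysis is unaffected. The correction is worth making because the output is already planned, the difference is undisclosed and the change is small.

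**What to change.** Before database lock, reconcile SAP 9.3.1 limb 1 with the laboratory criteria in protocol 9.3.3:

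- restrict it to patients with normal baseline AST/ALT and bilirubin;
- require concurrent values, and define concurrent (the protocol gives no window, so same sample or a stated interval would each need to be declared);
- use ALT or AST ≥3×ULN, bilirubin ≥2×ULN, and ALP ≤2×ULN or not available;
- route every patient with an abnormal baseline through limb 2 only, and align its bilirubin cut-off (>3×ULN in the protocol, ≥3×ULN in the SAP).

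Label the table and listing as potential Hy's law laboratory cases, with hemolysis and other causes left to clinical review of flagged patients. State and justify in SAP Section 10 any difference that is kept on purpose.

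The cost is a few lines of SAP text and a small programming change. No new data are needed.

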# 9.2. Criteria for Starting Cycle 1 and Each Subsequent Dose

Patients must meet all the following criteria to receive study treatment on Cycle 1 Day 1:

- ANC >  $1.5 \times 10^9$ /L
- Platelet count ≥100 × 10^9/L

- Total bilirubin ≤1.5 × ULN
- AST/ALT  $\leq 3 \times ULN$  or  $\leq 5 \times ULN$  in the presence of liver metastasis
- Other nonhematologic drug-related toxicities must be ≤ Grade 1 (except alopecia or peripheral neuropathy that may be Grade 2 or less).

G1T28-213

Patients must also have ANC  $\ge 1.5 \times 10^9 / L$  to receive any Cycle Day 1 dose of study treatment and ANC  $\ge 1.0 \times 10^9 / L$  to receive any Cycle Day 8 dose of study treatment.

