All cases confirmed on repeat testing as meeting the laboratory criteria defined above, with no other cause for liver function test (LFT) abnormalities identified at the time should be considered potential Hy's Law cases irrespective of availability of all the results of the investigations performed to determine etiology of the abnormal LFTs. Such potential Hy's Law cases should be promptly reported as SAEs via the EDC.

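### For patients who enter the SAP's second Hy's law limb through raised ALT or AST alone, the bilirubin test has no floor, so a normal bilirubin can count as Hy's law

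*SAP*

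**What the plan says.** SAP 9.3.1 (Abnormal Hepatic Laboratory Values) counts any occurrence among on-treatment, post-baseline assessments. Its Hy's law category has two limbs.

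- **First limb:** ALT and/or AST above 3 × ULN, with "alkaline phosphatase (ALP) < 2xULN, and total bilirubin ≥ 2xULN".
- **Second limb, entry:** "Preexisting baseline ALT, AST, OR total bilirubin values above the upper limit of normal". One raised test is enough, so bilirubin itself may be normal.
- **Second limb, transaminases:** "AST or ALT ≥ 2 times the baseline values and" at least 3 × ULN, or at least 8 × ULN, whichever is smaller.
- **Second limb, bilirubin:** concurrent "with total bilirubin ≥ 2 times the baseline value OR" at least 3 × ULN, whichever is smaller. Nothing requires the value to exceed ULN, and ALP is not mentioned.

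SAP 9.3.2 reports the number and percentage of patients in each hepatic category and adds a separate listing of patients who met Hy's law.

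Protocol 9.3.3 has the same baseline-relative bilirubin rule for patients with a raised baseline test: "Concurrent with total bilirubin increased by one time the baseline value OR >3 × ULN (whichever is smaller"). There it triggers further evaluation. Before a patient is considered a potential Hy's law case, the protocol adds a step that the SAP derivation does not carry: "All cases confirmed on repeat testing as meeting the laboratory criteria defined above, with no other cause" found for the liver test abnormality. Such cases are then reported as SAEs.

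**The concern.** A threshold set relative to baseline bilirubin makes allowance for a bilirubin that was already raised. Here it is also applied to patients whose bilirubin was normal and who enter the limb only through ALT or AST. For them it works in reverse: the lower the baseline bilirubin, the easier the test. The transaminase condition in the same limb has a floor of 3 × ULN; the bilirubin condition has none.

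A programmer following the SAP exactly would count a patient whose bilirubin never left the normal range as a Hy's law case. The output would also look inconsistent. The SAP's separate bilirubin rows start above 1.5 × ULN, so this patient would appear under Hy's law and in neither bilirubin row.

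**Working it through.** The plan gives no figure to reproduce here, so the check applies the rules as written. All values are multiples of ULN.

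**Inputs**
- First limb: ALT or AST > 3, ALP < 2, bilirubin ≥ 2 (SAP 9.3.1).
- Second limb, bilirubin threshold: min(2 × baseline bilirubin, 3) (SAP 9.3.1).
- Second limb, ALT or AST threshold: min(max(2 × baseline, 3), 8) (SAP 9.3.1).
- Bilirubin at Cycle 1 Day 1: "Total bilirubin ≤1.5 × ULN" (Protocol 9.2).
- ALT and AST at Cycle 1 Day 1: up to 3, or up to 5 with liver metastasis (Protocol 9.2).
- Patients: 30 (SAP 1.3).

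**Step 1: which alternative sets the bilirubin threshold.** Baseline bilirubin is at most 1.5, so 2 × baseline is at most 2 × 1.5 = 3.0. The 3 × ULN alternative therefore never lowers the threshold, and the multiple of baseline always decides.

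**Step 2: threshold by baseline bilirubin.**

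| Baseline bilirubin | Second-limb threshold | Compared with first limb (2.0) | Can a normal value qualify? |
|---|---|---|---|
| 0.3 | 0.6 | lower | yes |
| 0.4 | 0.8 | lower | yes |
| 0.5 | 1.0 | lower | yes, at ULN exactly |
| 0.75 | 1.5 | lower | no |
| 0.9 | 1.8 | lower | no |
| 1.0 | 2.0 | equal | no |
| 1.2 | 2.4 | higher | no |
| 1.5 | 3.0 | higher | no |

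The second limb is looser than the first for every baseline bilirubin below ULN. A value within the normal range can qualify only when 2 × baseline ≤ 1, that is, baseline ≤ 0.5.

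**Step 3: worked patients.**
- *Baseline ALT 2.0, bilirubin 0.4; later ALT 4.0, bilirubin 0.8.* ALT threshold: min(max(4.0, 3), 8) = 4.0, met. Bilirubin threshold: min(0.8, 3) = 0.8, met. The second limb is satisfied. The first is not, because 0.8 < 2.
- *Liver metastasis, baseline ALT 4, bilirubin 0.3; later ALT 8, bilirubin 0.6, ALP 5.* ALT threshold: min(max(8, 3), 8) = 8, met. Bilirubin threshold: 0.6, met. The second limb is satisfied. The first fails on both bilirubin and ALP.

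**Step 4: size in the table.** One such patient is 1/30 = 3.3%.

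**Step 5: how likely one is.** The documents give no frequency for this combination. For an assumed per-patient probability p, the chance of at least one in 30 is 1 − (1 − p)^30: 14% for p = 0.5%, 26% for 1%, 45% for 2%, 60% for 3% and 79% for 5%. These values of p are assumptions, not estimates.

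**The case against.** The best defence is that thresholds varying with baseline are deliberate. Protocol 9.3.3 says that the threshold depends on the patient's own baseline values and underlying conditions, and a sensitive screen is a reasonable choice for deciding whom to evaluate. That stands for the protocol, where the laboratory trigger is followed by repeat testing and a search for other causes. It does not carry over to the SAP, which turns the trigger into a counted category without that step.

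A second defence is that a wrong flag errs on the cautious side and could be seen. The Hy's law patients are listed, laboratory values carry reference-range flags, and bilirubin has its own rows. This also stands, and it is the main reason the point is minor. The count in the table would still be wrong.

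Three stronger readings are tempting, and the documents do not support them:
- *The output will contain false cases.* One patient would need raised baseline ALT or AST, baseline bilirubin at or below 0.5 × ULN, the required transaminase rise and a concurrent doubling of bilirubin to a value still within normal. Protocol 4.3.3.1 reports only generally low-grade, transient rises in AST, ALT or bilirubin in about 5% of patients.
- *Such patients are to be expected.* The entry criteria make raised transaminases eligible. They say nothing about how often this combination occurs.
- *One false case would overturn the statement that no Hy's law case has been reported with trilaciclib.* That statement in Protocol 4.3.3.1 describes earlier experience, and the listed values would show a normal bilirubin beside the flag.

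**Conclusion.** The SAP rule is wrong as written. For a patient who enters the second limb only through ALT or AST, its bilirubin threshold is below the first limb's 2 × ULN whenever baseline bilirubin is below ULN. It falls at or inside the normal range only when baseline bilirubin is at or below 0.5 × ULN; between 0.5 and 1.0 × ULN the rule is looser but still needs a value above ULN. No other SAP text prevents a patient with normal bilirubin from being tabulated and listed.

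The table and listing can therefore include such a patient, at 3.3% of 30 for each one; how likely this is cannot be derived from the documents. The result assumes that the SAP text is programmed literally and that the bilirubin limit at first dose is respected. Severity is minor: this is one descriptive safety category, and the primary endpoint is untouched.

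**What to change.** For the SAP tabulation only:

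1. In SAP 9.3.1, apply the multiple of baseline bilirubin only when baseline bilirubin was above ULN. Otherwise use the first limb's bilirubin ≥ 2 × ULN, whatever the baseline ALT or AST. Under this rule the first worked patient (bilirubin 0.8 × ULN) leaves the count.
2. Label the category *potential Hy's law (laboratory criteria)*.
3. List separately the patients who meet only the current wording, with their ALP, repeat-test result and any alternative cause, so that no case triggered under the protocol is lost.

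Protocol 9.3.3 governs patient evaluation and SAE reporting. It and the SAP must be reconciled; this review does not propose what the clinical trigger should be.

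The cost of the SAP change is a few lines of text and programming, with no new laboratory measurements.
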